18.4. Serious adverse events (SAE)

A serious adverse event is an adverse event that:

- Led to death,

- Led to a serious deterioration in the health of the subject, users or other persons as defined by one or more of the following:
 - 1) a life-threatening illness or injury, or
 - 2) a permanent impairment of a body structure or a body function including chronic diseases, or
 - 3) in-patient or prolonged hospitalization, or
 - 4) medical or surgical intervention to prevent life-threatening illness or injury or permanent impairment to a body structure or a body function.
- Led to fetal distress, fetal death or a congenital abnormality or birth defect.

This includes device deficiencies that might have led to a serious adverse event if:

- Suitable action had not been taken, or
- Intervention had not been made, or
- Circumstances had been less fortunate.

These are handled under the serious adverse event reporting.

Planned hospitalization for a pre-existing condition, or a procedure required by the CIP, without serious deterioration in health, is not considered a serious adverse event.

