18.5. Medical care of subjects

Principal investigator shall ensure that adequate medical care is provided to a subject experiencing an adverse event during and after participation in the clinical investigation. All serious adverse events will be followed until a resolution is addressed.

The current status of all ongoing adverse events is documented during site close-out.

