18.7. Investigator's reporting responsibilities

PI at each site must assess all (S)AE's that occur at his/her site.

- All serious adverse events and serious adverse device effects must be reported to sponsor within 24 hours of the site becoming aware of the event.
- A device deficiency that could have led to a serious adverse event but did not because suitable action was taken, intervention had been made or because of fortunate circumstances should be reported to sponsor within 24 hours of the site becoming aware of the event.

- New findings and/or updates in relation to already reported serious events should also be reported to sponsor within 24 hours of the site becoming aware of the event.
- Device deficiencies and all adverse device effects must be reported to sponsor within 10 days of becoming aware of the event.

When reporting the SAE, the relationship to the test material shall be described whether the event is considered

- **Not related**, the event has no temporal relationship with the use of the test material or the procedures.
- **Unlikely related**, the relationship with the use of the test material seems not relevant and/or the event can be reasonably explained by another cause, but additional information may be obtained.
- **Possibly related**, the relationship with the use of the test material is weak but cannot be ruled out completely. Alternative causes are also possible (e.g., an underlying or concurrent illness/ clinical condition or/and an effect of another device, drug, or treatment). Cases where relatedness cannot be assessed, or no information has been obtained should also be classified as possible.
- **Probably related**, the relationship with the use of the test material seems relevant and/or the event cannot reasonably be explained by another cause, but additional information may be obtained.
- **Definitely related/Causal relationship**, the event has a temporal relationship with the test material use/application or procedures.

The investigator will assess intensity for each AE and SAE reported during the investigation and assign it to one of the following categories:

- **Mild**, the intensity of the event is mild with no further action or intervention
- **Moderate**, the intensity of the event will lead to an action or intervention to solve the event
- **Severe**, the intensity of the event will lead to follow up on the action or intervention, as the effect of the action or intervention may not decrease the symptoms.

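### The adverse-event intensity grades in section 18.7 rest on action and follow-up, so they overlap, leave a gap and need not rank events by intensity

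*Combined protocol and SAP*

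**What the plan says.** Section 18.7 states the task: "The investigator will assess intensity for each AE and SAE reported during the investigation". It then gives three categories.

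- The lowest grade, Mild, sets two conditions at once: "the intensity of the event is mild with no further action or intervention".
- The middle grade, Moderate, turns on treatment being given, with no symptom level named: "the intensity of the event will lead to an action or intervention to solve the event".
- The top grade, Severe, applies where further checking is needed after treatment has been given; the plan's words are "the intensity of the event will lead to follow up on the action or intervention". The reason it offers is a possible lack of benefit from treatment, not an observed one.

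Two other sections make follow-up a routine duty. Section 18.5 says: "All serious adverse events will be followed until a resolution is addressed". Section 7.4 requires any adverse device effect, serious or not, that is still open when the study ends to be followed until it resolves.

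Seriousness is defined separately in section 18.4. Section 10.1.5 plans a listing of AEs, with a summary where relevant, and specifies no analysis by intensity.

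**The concern.** An intensity scale should be ordered and should give each event one grade. In section 18.7 the two upper grades are told apart by what was done about the event, with no description of symptom level or effect on daily life. The lowest grade repeats the word it defines. Elsewhere the protocol uses intensity in the ordinary sense: section 18.2 judges redness by whether its intensity falls within minutes of removing the baseplate.

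At stake is whether the grade attached to each AE and SAE can be read as intensity. If two investigators can grade the same event differently and both comply, or can find no grade that fits, the intensity column in the safety listing and any table built on it are unreliable.

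**Working it through.** No arithmetic applies, and the plan gives no figure to reproduce. The check applies the three definitions literally to each combination of intensity (mild or not) and management (none, action, action with follow-up). It assumes that any action or follow-up arises from the event's intensity, as the definitions require.

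| Intensity | Management | Mild? | Moderate? | Severe? | Grade |
|---|---|---|---|---|---|
| Mild | None | Yes | No, no action | No, no action to follow up | Mild |
| Mild | Action | No, action taken | Yes | No | Moderate |
| Mild | Action and follow-up | No, action taken | Yes | Can be met | Moderate or Severe |
| Not mild | None | No, intensity not mild | No, no action | No, no action to follow up | None |
| Not mild | Action | No | Yes | No | Moderate |
| Not mild | Action and follow-up | No | Yes | Can be met | Moderate or Severe |

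Of the six combinations, three have one grade, two have two possible grades and one has none.

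**Overlap.** Severe adds to Moderate only the follow-up and the possibility that the action will not help. The second part is worded as a possibility, so treatment need not have failed. Sections 18.5 and 7.4 require follow-up of all SAEs and of device effects still open at study end. For those events, the presence of follow-up does not separate the two grades.

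**Gap.** A non-mild event with no intervention fails all three definitions, yet the investigator must assign one. Such events are plausible here. Section 7.7 bars barrier products throughout and topical steroids on the peristomal skin, so a troublesome skin event may receive no action.

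**Order.** A minor event that is treated, persists and is followed up can be graded Severe (third row). A more intense event that is treated successfully can be graded Moderate (fifth row). The second and fifth rows receive the same grade although their intensity differs.

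**Where the grade is used.** The 24-hour and 10-day deadlines in section 18.7, and the sponsor's 7-day and 2-day deadlines in section 18.8, turn on seriousness, device effect, device deficiency or imminent risk, not on Mild, Moderate or Severe. Section 10.4 rests pass or fail on the primary endpoint alone.

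**The case against.** The strongest reply is that the scale does refer to intensity. Mild names it, and the other two grades are phrased as what the intensity will lead to, so management may be meant as a marker of intensity. That stands as a reading of the intent, and it rules out saying that intensity plays no part. It does not supply a grade for a non-mild untreated event or a boundary between the upper two grades.

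A reader might infer several stronger points that the documents do not support.

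- That an intense untreated event is graded Mild. It is not, because Mild requires mild intensity. The event has no grade.
- That an SAE qualifying through "medical or surgical intervention to prevent life-threatening illness or injury" must be Moderate once treatment works. Moderate is possible, but Severe is also open because every SAE is followed. An event that is "a life-threatening illness or injury, or" otherwise meets section 18.4 is an SAE whatever its grade.
- That the grade biases a severity comparison between products because the trial is open-label (section 5.7). No such comparison is planned. A symptom-based grade would also be assigned by someone who knows the product worn, so unblinding is not an argument for the change.
- That safety oversight relies on the grade. Section 18.9 lists what the Medical Advisor receives and does not mention it. Severity in sections 18.4.2 and 18.4.3 refers to the risk analysis report, not to this scale.

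It can also be said that skin symptoms are measured elsewhere: pain, itching and burning on 0-10 scales at each baseplate change (Appendices 1 and 4), and daily-life impact by the DLQI at visits. That is true and lowers the stakes for skin events. It does not cover other AEs, and it does not repair the AE grade itself.

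**Conclusion.** The point holds as a defect in a stated rule. The categories in section 18.7 overlap for treated events that are followed up, omit non-mild events without intervention, and can reverse the order of a minor persistent event and a more intense one treated successfully. Reversal is possible under the wording but not forced by it.

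The size is modest. A grade is required for every AE and SAE among the 82 planned subjects, but the documents give no event counts or treatment rates, so the share affected cannot be derived. The effect is confined to descriptive safety data: the grade in the AE listing and any summary. SAE status, reporting deadlines and the primary endpoint are untouched.

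The conclusion rests on a literal reading of section 18.7. The AE form and the training material are not in the documents. If they define the grades more fully, the protocol wording should be brought into line with them.

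**What to change.** Replace the three definitions in section 18.7 with ones based on symptom burden or interference with usual activities:

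- Mild: noticed, but does not interfere with usual activities.
- Moderate: interferes with usual activities.
- Severe: prevents usual activities.

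Add a sentence saying where an event without symptoms belongs, since section 18.1 counts abnormal laboratory findings as AEs. Make sure that action taken and outcome are separate fields on the AE form, if they are not already, so that the management information now mixed into the grade is kept.

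The cost is a small change to wording, form labels and investigator training. Treatment, endpoints, sample size and reporting duties do not change. Grades would no longer be comparable with any other study that used the present scale, but the documents name no such study.

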18.8. Sponsors Reporting Responsibilities

It is the responsibility of sponsor to ensure that the following are reported to national regulatory authorities immediately, but no later than 7 calendar days following the date of awareness by sponsor.

- All serious adverse events.
- All serious device effects.
- All device deficiencies that could have led to serious adverse events but did not because suitable action was taken, intervention had been made or because of fortunate circumstances.
- New findings and/or updates in relation to already reported events.

If the serious adverse event results in imminent risk of death, serious injury, or serious illness that requires prompt remedial action for other subjects, users or other persons or a new finding to such a serious adverse event, sponsor must immediately but no later than 2 calendar days after awareness by sponsor report the event to national regulatory authorities and ethics committees, as applicable.

It is the responsibility of sponsor to inform all investigators in writing within 10 working days if device deficiencies, adverse events, adverse device effects, near-incidents, serious adverse events, serious adverse device effects or unanticipated serious adverse device effects lead to corrective actions (e.g., change of IFU).

18.9. Medical Advisor Safety Review

The Sponsor is responsible for ensuring all Serious Adverse Event (s) are provided to the Medical Advisor for review and discussion.

The Medical Advisor will be informed of the following:

- All serious adverse events related to the investigation product or clinical investigation and serious adverse device effects
- A device deficiency that could have led to a serious adverse event but did not because suitable action was taken, intervention had been made or because of fortunate circumstances
- New findings and/or updates in relation to already reported serious events

In addition, the Medical Advisor will receive lists of any reported AE's and ADE's related to the investigation product or clinical investigation, as defined by sponsor for a review of safety.

Correspondence, decisions, and recommendations regarding safety in the Clinical Investigation from the Medical Advisor must be documented and saved electronically in the Sponsor File.

18.10. Data Safety and Monitoring Board (DSMB)

The review of all safety data will be conducted on an ongoing basis to identify any potential safety issues. If needed, the Medical Advisor can call for a Data Safety and Monitoring Board meeting with relevant members, to discuss potential safety issues and further recommendations, if relevant.

Based on the safety data review, the Medical Advisor along with the DSMB may recommend that the sponsor modifies, temporarily suspends, or terminates the clinical investigation.

Correspondence, decisions, and recommendations regarding safety in the Clinical Investigation from the Data Safety and Monitoring Board must be documented in meeting minutes and saved electronically in the Sponsor File.

All final decisions, however, regarding clinical investigation modifications, remain with the Sponsor.

19. Suspension or premature termination of the clinical investigation

Sponsor may suspend or prematurely terminate an investigation site or the entire clinical investigation for documented significant reasons.

If a suspicion of an unacceptable risk to subjects develops during the clinical investigation, sponsor will suspend the investigation while the risk is assessed. Sponsor will terminate the investigation if an unacceptable risk is confirmed. Sponsor will ensure that the premature termination will be justified in writing and will promptly inform the regulatory authorities and relevant EC(s). If monitoring or auditing of the clinical investigation identifies serious or repeated deviations at one of the participating investigation sites, sponsor will suspend or terminate the particular investigation site. The sponsor or investigator will inform the regulatory authority as appropriate and notify the EC about the termination of the site.

If suspension or termination of the clinical investigation occurs, the investigator(s) will promptly inform the enrolled subjects. Sponsor will provide resources to fulfil the obligations from the CIP for follow-up of the subjects, as necessary.

20. Clinical investigation report

At completion of the investigation sponsor is responsible for writing the clinical investigation report. The report is retained on file. The report contains a critical evaluation of all data, which have been collected during the investigation. The report describes the methodology and design and a data analysis, including statistical preparation and conclusion.

Sponsor and national coordinating investigators must sign the final version of the clinical investigation report or an affidavit, indicating their agreement with the contents. If no coordinating investigators are appointed, then the signatures of the principal investigators should be obtained.

The clinical investigation report must be submitted to EC and regulatory authorities.

21. Publication policy

The results of the investigation, positive as well as negative, may be communicated by abstracts, posters, or oral presentations provided that opportunity is given for sponsor to discuss the contents and any conclusions drawn, before the abstract, paper, or visual presentations are finalised. In all cases the subject's identity will remain confidential.

Sponsor will undertake to comment on the draft documents within 30 working days of receipt, but the final decision on the contents and format of the publication from the conclusions drawn, will remain with the authors.

No preliminary results will be published (if sub studies are performed using an umbrella CIP, results and conclusions for each sub investigation can be published).

Data from the investigation is considered confidential until it is published according to the conditions of this CIP.

Sponsor may publish single subject case stories at any time during and after the investigation.

Sponsor reserves the right to use the data (published and unpublished) for reimbursement or regulatory purposes.

22. Suspension/termination of the clinical investigation

Sponsor will withdraw from sponsorship of the clinical investigation if:

- major non-adherence to the clinical investigation plan is occurring
- it is anticipated that the subject recruitment will not be adequate to meet the investigation objectives [at least 75%] of the subjects should be entered within the recruitment time.

In case sponsor withdraws, sponsorship for the subjects already recruited into the clinical investigation will continue.

23. Appendices

Appendix 1: Ostomy Skin Tool V2.0 - Decision Tree Score

The PRO data from OST V2.0 and the image analysis data are combined in a Decision Tree model to provide an overall skin complications severity level for each patient. The Decision Tree model provides a hierarchy of scores and assigns patients a skin severity level based on the observed combination of these variables, as outlined below.

*Pain, itching, and burning severity items on a scale from 0-10 mapped together constitutes the PIB score, which is the highest value of pain, itching and burning

Appendix 2: Dermatology Life Quality Index Questionnaire

(<https://www.cardiff.ac.uk/medicine/resources/quality-of-life-questionnaires/dermatology-life-quality-index>)

The aim of this questionnaire is to measure how much your skin problem has affected your life
OVER THE LAST WEEK. Please tick one box for each question.

[figure not shown]
1. Over the last week, how **itchy, sore, painful or stinging** has your skin been?
Very much A lot A little Not at all
2. Over the last week, how **embarrassed** or **self conscious** have you been because of your skin?
Very much A lot A little Not at all
3. Over the last week, how much has your skin interfered with you going **shopping** or looking after your **home** or **garden**?
Very much A lot A little Not at all Not relevant
4. Over the last week, how much has your skin influenced the **clothes** you wear?
Very much A lot A little Not at all Not relevant
5. Over the last week, how much has your skin affected any **social** or **leisure** activities?
Very much A lot A little Not at all Not relevant
6. Over the last week, how much has your skin made it difficult for you to do any **sport**?
Very much A lot A little Not at all Not relevant
7. Over the last week, has your skin prevented you from **working** or **studying**?
If "No", over the last week how much has your skin been a problem at **work** or **studying**?
Yes No Not relevant
A lot A little Not at all Not relevant
8. Over the last week, how much has your skin created problems with your **partner** or any of your **close friends** or **relatives**?
Very much A lot A little Not at all Not relevant
9. Over the last week, how much has your skin caused any **sexual difficulties**?
Very much A lot A little Not at all Not relevant
10. Over the last week, how much of a problem has the **treatment** for your skin been, for example by making your home messy, or by taking up time?
Very much A lot A little Not at all Not relevant

© AV Fulayek GK Khan, April 1992, www.terminology.org.uk, this must not be copied without the permission of the authors.

Please check you have answered EVERY question. Thank you.

Appendix 3: CP338 Endpoints and Assessments

	Endpoints and assessment	Assessed by	V1	V2	V3	Follow-up calls (Call 1-4)	Baseplate/ Product change
Primary endpoint	Decision Tree Score on baseplate level at steady state (scale from 0-3) Skin condition Ostomy Skin Tool V2.0 (Appendix 1 and 4)	Sponsor, based on subject reported outcomes via Ostomy Skin Tool and discoloration area					X
Secondary endpoint	Health-related quality of Life (DLQI) score evaluated at the end of each test period (scale from 0-30) (DLQI questionnaire, Appendix 2)	Subject	X	X	X	X	X
			X	X	X	X	X

Appendix 4: Ostomy Skin Tool V2.0 – PRO (Patient Reported Outcome) Questionnaire
 The OST V2.0 comprises a PRO questionnaire consisting of six items designed to assess the severity of peristomal skin complications.

Patient questionnaire		Patient questionnaire																							
Patient number: _____	Date: ___ / ___ / ___	Patient number: _____	Date: ___ / ___ / ___																						

Instructions
 
These questions should be completed by the patient themselves. The following questions ask about the skin complications you experience around your stoma (from the stoma site to the edge of the stoma bag adhesive). Please answer each question thinking about right now when changing your product.
 
Question 1. Do you experience any bleeding from the skin around your stoma right now when changing your product? (tick one box only)
 
 
 	Experiencing		Not experiencing	
 
 
Question 2. Once you have cleaned and dried the skin, do you still experience any weeping or moisture on the skin around your stoma right now when changing your product? (tick one box only)
 
 
 	Experiencing		Not experiencing	
 
 
Question 3. Are you experiencing any ulcers or sores around your stoma right now when changing your product? (tick one box only)
 
 
 	Experiencing		Not experiencing	
 
					Experiencing		Not experiencing		Experiencing		Not experiencing		Experiencing		Not experiencing										
	Experiencing		Not experiencing																						
	Experiencing		Not experiencing																						
	Experiencing		Not experiencing																						

Instructions
 
The following questions ask about the skin complications you experience around your stoma (from the stoma site to the edge of the stoma bag adhesive). Please answer each question thinking about the period since you last changed your product until now.
 
Question 4. Please rate on a scale from 0-10 how itchy the skin around your stoma has been at its worst since you last changed your product. (tick one box only)
 
 
 	0 No itch		1 Very mild itch		2		3		4		5		6		7		8		9		10 Worst possible peristomal skin itch	
 
					0 No itch		1 Very mild itch		2		3		4		5		6		7		8		9		10 Worst possible peristomal skin itch
	0 No itch		1 Very mild itch		2		3		4		5		6		7		8		9		10 Worst possible peristomal skin itch				

Please turn over
		
Modified OST PRO Version 12_0 Page 1
																							

Modified OST PRO Version 12_0 Page 2
		
Modified OST PRO Version 12_0 Page 2
																							

